	
 - Patients who are considered not to be eligible for this study by their investigator or sub-investigator
Study drug:	
(1) Dosage Form : Film coat tablet Suvorexant 15mg tablet/20mg tablet, Placebo 15mg tablet/20 mg tablet
 
(2) Package : Suvorexant 15mg tablet: 21 tablets in a plastic bottle Suvorexant 20mg tablet: 21 tablets in a plastic bottle Placebo 15mg tablet: 21 tablets in a plastic bottle Placebo 20mg tablet: 21 tablets in a plastic bottle
 
(3) Storage : Investigational products are to be stored at room temperature. Store in the bottle just before taking to protect from light and moisture.

Study design:	
This study is a multi-center, double blind, randomized, parallel design.
  
The diagram illustrates the study design timeline. It starts with a 'Run-in period' leading to 'Visit 1'. Following 'Visit 1' is a '5 days before Visit 2' period. 'Visit 2 (Week 0)' is marked with a downward arrow indicating 'Randomization if morning SBP ≥ 135mmHg by HbPM'. This leads to the 'Treatment period' with 'Visit 3' and 'Visit 4 (Week 2)'. A blue arrow at the top indicates 'Unchanged antihypertensive medication throughout the study periods'. Red arrows at the bottom indicate 'Home blood pressure monitoring (morning and evening)' and 'ABPM' (Ambulatory Blood Pressure Monitoring) at Visit 1 and Visit 4.

Outcomes	
Primary Outcome :
 
 - Change in sleep systolic blood pressure (BP) at week 2 from week 0 by ambulatory blood pressure monitoring (ABPM) 
Secondary Outcomes :
 
 - Percent of patients changed from the non-dipper to the dipper during the treatment period - Change in morning SBP at week 2 from week 0 by ABPM and home blood pressure monitoring (HbPM) - Change in standard deviation (SD) and coefficient of variation (CV) of sleep SBP at week 2 from week 0 by ABPM - Change in the total sleep time - Change in the time to sleep onset - Correlation of changes in nighttime BP parameters with changes in sleep quality parameters - Correlation of changes in urinary albumin-to creatinine ratio (UACR)/NT-proBNP
Study size:	80 patients in total

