Statistical Analysis:	
Study size calculation:
 
At 80% power and assuming adjusted mean differences in the change from baseline in mean nighttime SBP with suvorexant vs placebo of -5.0 mm Hg with a standard deviation (SD) of 7.5 mm Hg in both groups, it was calculated that 36 patients in each group would be required (72 in total). The target enrollment was set at 80 patients to allow for a 10% withdrawal rate.
 
Statistical analysis methods:
 
All analyses will be conducted in the full analysis set (FAS), which included all enrolled participants who received their assigned therapy at least once after randomization and who had made 24 - hour ABPM recordings at least once. The safety analysis set (SAS) included all randomized participants who had received the assigned therapy at least once during the study period. Efficacy analyses for BP values will be conducted in the FAS, and safety will be determined in the SAS.
 
Intergroup comparisons will be tested with a t-test for continuous variables, and Pearson's chi-squared test or Fisher's exact test will be used for dichotomous data. Mixed - effects model repeated measures (MMRM) analysis will be used to compare the changes in SBP. MMRM included the randomized study group, the time points (baseline, week 2), the interaction between the study group and time points as fixed effects, and age and sex as covariates. P - values for interactions between baseline SBP and the change from baseline in SBP will be determined using the general linear model, adjusted for age and sex. All statistical analyses will be performed with SAS version 9.4 software (SAS Institute Inc, Cary, NC, USA). P - value is two - tailed, and its <0.05 is considered statistically significant.

-----------------------	--

Schedule of examination, observation and assessment

	Run-in period ^{※1}	Treatment period			Termination
	Visit 1	Visit 2	Visit 3	Visit 4	
	- 4 week	Week 0	Week 1	Week 2	
Informed consent	○				
Pre-enrollment ^{※2}	○				
Enrollment ^{※2}		○			
Randomization		○			
Administration of study drug ^{※3}			←————→		
Study drug adherence				○	○
Concomitant medications	○	○	○	○	○
Demographic characteristics	○				
Subjective symptoms, Objective findings	○	○	○	○	○
Height, Weight, Abdominal circumference ^{※4}	○	○		○	○
Home blood pressure monitoring (morning, evening) ^{※5}		←————→			
Clinic blood pressure monitoring	○	○	○	○	○
Ambulatory blood pressure monitoring (ABPM) ^{※6}		○		○	○ ^{※9}

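### One P<0.05 rule covers the primary and seven between-arm secondary comparisons alike, so a trial with a null primary can still declare a significant secondary, with a false-positive chance of up to about 30%

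*Combined protocol and SAP*

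**What the plan says.** The synopsis names a single primary outcome: "Change in sleep systolic blood pressure (BP) at week 2 from week 0 by ambulatory blood pressure monitoring (ABPM". The sample size rests on that comparison alone: "At 80% power and assuming adjusted mean differences in the change from baseline in mean nighttime SBP", with a difference for "suvorexant vs placebo of -5.0 mm Hg with a standard deviation (SD) of 7.5 mm Hg in both groups".

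The secondary list under Outcomes contains seven comparisons that can each be tested between arms:

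1. conversion from non-dipper to dipper;
2. and 3. morning SBP by two methods: "Change in morning SBP at week 2 from week 0 by ABPM and home blood pressure monitoring (HbPM";
4. and 5. two variability measures: "Change in standard deviation (SD) and coefficient of variation (CV) of sleep SBP at week 2 from week 0 by ABPM";
6. total sleep time;
7. time to sleep onset.

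Two correlation outcomes follow, and the Statistical Analysis section adds interaction P-values involving baseline SBP.

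That section closes with one threshold: "P - value is two - tailed, and its <0.05 is considered statistically significant". It comes directly after the statement on the software for all analyses. The documents give no testing order, multiplicity adjustment or gate on the primary, and no statement that secondary results are exploratory or supportive.

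**The concern.** Unadjusted secondaries are common and do little harm when the plan says they are supportive. This plan does not say so, and the stated rule attaches the same label to any P below 0.05.

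It matters more than usual here because the title and objective name two targets, sleep blood pressure and circadian rhythm. The primary covers the first. The second is reached only through secondaries, most directly dipper conversion. If sleep SBP shows no effect, the plan as written still lets the trial report a statistically significant effect on dipping status, morning SBP or SBP variability. Nothing would tell the reader that this was one of several unadjusted tests in a trial sized for something else.

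**Working it through.** **The plan's own figure.** Inputs from the study size calculation: difference 5.0 mmHg, SD 7.5 mmHg, power 80%; two-sided 5% from the closing rule.

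n per arm = 2 × (1.960 + 0.842)² × 7.5² / 5.0² = 35.3, rounded up to 36, so 72 in total; 72 / 0.90 = 80. This reproduces the plan. A one-sided 5% test would need only 28 per arm, so the figure rests on one two-sided 5% test of one outcome. The documents give no error rate for the secondaries.

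**Independent secondaries, all nulls true.**

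- Seven tests: 1 − 0.95⁷ = 30.2%.
- Only the five blood-pressure tests null: 1 − 0.95⁵ = 22.6%.
- Seven tests, counting only false findings in the drug's favour: 1 − 0.975⁷ = 16.2%.

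**Correlated secondaries, given a non-significant primary.** The documents give no correlations, so every value below is an assumption. Eight test statistics (the primary and seven secondaries) were drawn from a multivariate normal distribution with no treatment effect, 1,000,000 draws per scenario, keeping draws in which the primary was not significant at two-sided 5%. For the last column, statistics are signed so that favourable results correlate positively.

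| Assumed correlation | Any of seven | Any of the five BP tests | Any of seven, favouring drug |
|---|---|---|---|
| Common, 0.1 | 29.6% | 22.3% | 15.5% |
| Common, 0.2 | 28.2% | 21.4% | 14.4% |
| Common, 0.3 | 26.2% | 20.1% | 13.3% |
| Common, 0.5 | 21.0% | 16.5% | 10.5% |
| Common, 0.7 | 14.8% | 12.0% | 7.4% |
| Block A | 28.1% | 20.3% | 14.9% |
| Block B | 27.1% | 19.5% | 14.4% |
| Block C | 24.3% | 16.8% | 12.7% |

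Pairs not listed have zero correlation:

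- Block A: SD with CV 0.9.
- Block B: SD with CV 0.8; the two morning SBPs 0.4; the two sleep outcomes 0.3; primary with dipper conversion 0.4, ABPM morning SBP 0.5 and home morning SBP 0.3.
- Block C: the same pairs at 0.95, 0.6, 0.5, 0.6, 0.6 and 0.5; dipper conversion with ABPM morning SBP 0.3 and with home morning SBP 0.2.

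**Dipper conversion is binary.** The plan assigns such data to Pearson's chi-squared or Fisher's exact test. With 18 to 36 patients per arm and a true conversion rate of 10-30% (both assumed), Fisher's test has an actual size of 0.9-2.8%. Using that for one of seven independent tests gives 1 − 0.95⁶ × 0.991 = 27.2% to 1 − 0.95⁶ × 0.972 = 28.5%, instead of 30.2%.

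**Effect of control.** Bonferroni over seven tests (0.05 / 7 = 0.0071) gives 1 − (1 − 0.0071)⁷ = 4.9% under independence and 1.8-4.8% across the correlations tried. If a formal secondary test is allowed only after a significant primary, a failed primary permits no formal secondary claim, so the figure is zero.

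**The case against.** The strongest reply is that the plan already ranks its evidence: it names one primary and sizes the trial on that alone. The P<0.05 sentence is then a generic statement of software and threshold, and no section says that a secondary may rescue a failed primary. This stands in part. A reader might infer that the sponsor intends to claim success on a secondary, or that the trial's main conclusion is compromised. The documents support neither. They do not announce such a claim, and the single primary keeps its 5% error rate. What remains is that the rule as worded permits the claim and nothing rules it out.

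A second reply is that a figure near 30% is a ceiling. That is right. A reader might take 27-30% as a fixed property of any trial whose primary fails. It needs all seven nulls to be true, weak correlation, and errors counted in both directions. A null sleep-SBP result does not make total sleep time or sleep onset null in a trial of a sleep drug, so the five-test column is the fairer one for claims about circadian rhythm, morning SBP and variability.

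Two further inferences should be resisted. One is to add the correlation and interaction analyses to the count and quote a larger total. The documents do not give their number, and they do not describe them as between-arm efficacy tests. The other is that each closely related pair (SD with CV, ABPM with home morning SBP) gives a full second chance at 5%. The more nearly two measures duplicate each other, the less the second adds, which is part of why the total falls below 30%.

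**Conclusion.** The concern holds as a matter of how secondary results may be described. One unqualified 5% rule covers the primary and seven between-arm secondaries, with no gate, adjustment or exploratory label, while a co-named objective depends on secondaries only.

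Given a non-significant primary, the chance of at least one false significant secondary is:

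- up to about 30% if all seven nulls are true and independent, and roughly 15-30% over the assumed correlations;
- about 17-23% if only the five blood-pressure secondaries are null, under independence or block correlations (12% at a common correlation of 0.7);
- about 13-16% counting only findings in the drug's favour, again under independence or block correlations (7% at a common correlation of 0.7), against 2.5% for one direction of a single two-sided 5% test.

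These figures treat all tests as having their nominal size; Fisher's test for dipper conversion would lower them slightly. The need for a change does not turn on which correlation is right, since every scenario is well above the nominal level. This is a cheap improvement to the plan and not a defect in the primary analysis.

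**What to change.** Replace the closing significance sentence with wording such as: *The two-sided 5% significance claim applies to the primary outcome. Secondary outcomes, correlations and interaction analyses are supportive, and are reported as estimates with 95% confidence intervals and nominal P-values.*

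If a confirmatory statement on circadian rhythm is wanted, name one secondary outcome for it before unblinding and test it at two-sided 5% only if the primary is significant. This fixed order takes no alpha from the primary.

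The change is one or two sentences and needs no additional patients, visits or data. Its downside is that secondary results can no longer carry an unqualified significant label, including any that reflect a real effect.
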